For cohorts 1 to 8, imaging scan and disease assessment will be performed at screening/baseline and repeated every 8 weeks (56 days \pm 7 days) from the first dose of study treatment throughout the study until the subject has radiologically-confirmed disease progression, initiates a new subsequent anticancer therapy, dies, withdraws consent, is lost to follow-up or the study closes, whichever occurs first. After 1 year on study treatment, the frequency of disease assessment will be reduced to every 12 weeks (84 days \pm 7 days). Subjects in cohorts 1 to 8 who discontinue study treatment for reasons other than radiologically-confirmed disease progression by RECIST Version 1.1 will enter into a post treatment follow-up period and continue to receive imaging scans every 8 weeks (56 days \pm 7 days) until the subject has radiologically-confirmed disease progression, initiates a new anticancer therapy, dies, withdraws consent, is lost to follow-up or the study closes, whichever occurs first.

In cohort 9, the first on-study imaging will be performed 9 weeks (\pm 7 days) from the first dose of study treatment and then every 6 weeks (\pm 7 days) throughout the study until the subject has radiologically-confirmed disease progression (confirmed progressive disease [iCPD] per modified RECIST v1.1 for immune-based therapeutics [iRECIST]), initiates a new subsequent anticancer therapy, dies, withdraws consent, is lost to follow-up or the study closes, whichever occurs first. After 18 months on study treatment, the frequency of disease assessment will be reduced to every 9 weeks (\pm 7 days). Subjects in cohort 9 with unconfirmed progressive disease per iRECIST guidelines [Seymour et al, 2017] who are clinically stable may continue on study treatment until progression is confirmed by the investigator (iCPD) at the next imaging assessment 6 weeks (\pm 7 days) after iUPD. Treatment with pembrolizumab will be discontinued once the subject has received a maximum of 35 administrations of pembrolizumab (approximately 2 years).

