Efficacy analyses have shown that enfortumab vedotin demonstrates antitumor activity. In Study EV-101 (efficacy data cutoff: 25 Oct 2018), the confirmed ORR (complete response [CR] + partial response [PR]) in the metastatic UC 1.25 mg/kg dose group, was 42.9% (48 out of 112 subjects), including 5 subjects (4.5%) with CR and 43 subjects (38.4%) with PR. In Study EV-102 (date of last evaluation: 25 Feb 2019), the confirmed ORR was 35.3% (6/17 subjects). The majority of subjects had tumor shrinkage. In Study AGS-22M6E-11-1, (date of last evaluation: 27 Apr 2015), 9 subjects with various solid tumors were treated with enfortumab vedotin; 5 (55.6%) subjects achieved stable disease and 4 (44.4%) subjects had progressive disease. In Study EV-201 (data cutoff: 01 Mar 2019 for Cohort 1 and 08 Sep 2020 for Cohort 2), the confirmed ORR per blinded independent central review (BICR) assessment was 44% (55 of 125 subjects) in Cohort 1 (previously treated with a platinum-containing chemotherapy and a PD-1/PD-L1 inhibitor) and 52% (46 out of 89 subjects) in Cohort 2 (previously treated with a PD-1/PD-L1 inhibitor, platinum naïve and cisplatin ineligible). Per an FDA request, a later data cutoff date of 04 Dec 2020 was also used to provide an update to the DOR for Cohort 2 after all responders had been followed for at least 6 months from the onset of response. The updated confirmed ORR per BICR assessment was 51% (45 of 89 subjects); there was a loss of 1 responder when an equivocal new lesion identified at week 8 became unequivocal at a later time point. In Study EV-301 (data cutoff: 15 Jul 2020), the OS of subjects with locally advanced or metastatic UC treated with enfortumab vedotin was significantly prolonged on the enfortumab vedotin arm compared with the chemotherapy arm, with a 30% reduction in the risk of death (HR = 0.702, 95% CI: 0.556, 0.886; P = 0.00142, with a predetermined 1-sided significance level of 0.00679 based on the number of observed deaths). The median OS was 12.88 months for the enfortumab vedotin arm and 8.97 months for the chemotherapy arm.

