7.1.1 Imaging for Disease Assessment (Computed Tomography/Magnetic Resonance Imaging)

For cohorts 1 to 8, imaging/disease assessment will be performed at screening/baseline and every 8 weeks ($56 \text{ days} \pm 7 \text{ days}$) from the first dose of study treatment throughout the study until the subject has radiologically-confirmed disease progression, initiates a new subsequent anticancer therapy, dies, withdraws consent, is lost to follow-up or the study closes, whichever occurs first. Baseline imaging performed prior to informed consent as standard of care may be used as long as it is performed within 28 days prior to the first dose of study treatment.

Disease response and progression will be assessed by the investigator. If disease response is assessed as CR or PR by investigator, a confirmatory imaging scan is required 4 weeks ($28 \text{ days} + 7 \text{ days}$) after the first response. After 1 year on study treatment, the frequency of disease response assessments will be reduced to every 12 weeks ($84 \text{ days} \pm 7 \text{ days}$).

In cohort 9, the first on-study imaging/disease assessment will be performed 9 weeks ($63 \text{ days} \pm 7 \text{ days}$) from the first dose of study treatment and then every 6 weeks ($42 \text{ days} \pm 7 \text{ days}$) throughout the study. After 18 months on study treatment, the frequency of disease response assessments will be reduced to every 9 weeks ($\pm 7 \text{ days}$). Baseline imaging performed prior to informed consent as part of standard of care may be used as long as it is

performed within 28 days prior to the first dose of study treatment. Tumor imaging should also be performed whenever disease progression is suspected. Objective responses will be confirmed per RECIST Version 1.1 with repeat scans at least 4 weeks (+7 days) after first documentation of response.

Imaging for cohort 9 should include the head, neck, chest and abdomen at the specified timepoints. A CT from the vertex of the head to the thoracic inlet or a brain CT is strongly preferred. Imaging of the pelvis is optional.

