A CT scan with contrast is the preferred modality for tumor assessment. Magnetic resonance imaging is acceptable if local standard practice or if CT scans are contraindicated in a subject (e.g., subject is allergic to contrast media). All other RECIST-approved scanning methods such as x-ray are optional. The same imaging modality should be used throughout the study. Additional instructions for imaging assessments can be found in the study procedures manual.

The assessment will include tumor measurements for target lesions, nontarget lesions and any new lesions. A response assessment will be characterized for a given time point evaluation. At the end of study for each subject, the best overall response (BOR) to the study regimen will be derived. To ensure comparability, the screening and subsequent assessment of response should be performed using identical techniques. The same individual should assess images for any 1 subject for the duration of the study if possible.

The site of disease progression including target, nontarget and/or new lesions should be documented in the eCRF. Additional imaging may be performed at any time to confirm suspected progression of disease.

This study will be analyzed based on the results of local (investigator) radiological assessments. Copies of all imaging scans will also be sent to the independent review facility in a timely manner. Images at the independent review facility will be stored. Imaging scans for a cohort may be read at the independent review facility when the minimum number of responders per investigator assessment (subjects with confirmed CR and PR) to claim promising antitumor activity at stage 1 are met based on the 2-stage BOP2 design. Central images may also be read in certain circumstances as determined by the sponsor.

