5.2.3 Progression-free Survival per Investigator Assessment

PFS is defined as the time from the date of first dose of study drug to the date of first documented radiological disease progression (PD) per RECIST Version 1.1 by investigator assessment or death due to any cause, whichever comes first. PFS will be censored as the following:

- If a subject has neither PD nor death, PFS will be censored at the date of last evaluable radiological tumor assessment.
- If a subject starts a new anti-cancer treatment before any PD event or death, PFS will be censored at the date of last evaluable radiological tumor assessment prior to the date of new anti-cancer treatment.
- If a subject has PD or death immediately after two or more consecutive missed radiological tumor assessments, DOR will be censored at the last evaluable radiological tumor assessment prior to two or more missed radiological tumor assessments.
- If a subject does not have evaluable postbaseline radiological assessment, PFS will be censored at the first dose date of study drug.

For a subject who is censored, the last evaluable radiological tumor assessment refers to the subject's last radiological tumor assessment where the response is CR, PR or SD.

New anti-cancer treatment includes therapies captured on new anti-cancer therapy eCRF and new radiation/palliative radiation therapies captured on new radiation therapy eCRF that will impact target and/or non-target lesions.

PFS (in months) will be calculated as:

$$[(\text{Date of documented disease progression or death or censoring}) - (\text{Date of first dose of study drug}) + 1] / 30.4375$$

When a cutoff date is applied to PFS analysis, tumor assessment, death and new anti-cancer treatment occurring after the cutoff date will be excluded from the analysis.

The primary analysis population for PFS is FAS.

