5.3.2 Response Related Endpoints per RECIST Version 1.1 by Blinded Independent Central Review

Imaging scans for a cohort may be read at the independent review facility when the minimum number of responders per investigator assessment (subjects with confirmed CR or PR) at stage 1 are met based on the 2-stage BOP2 design. Central images may also be read in certain circumstances as determined by the sponsor. The following response related endpoints will be derived similarly as the corresponding endpoint per investigator assessment, except that timepoint tumor response per independent central review will be used.

- Confirmed ORR per BICR
- DOR per BICR
- DCR per BICR
- PFS per BICR
- BOR per BICR
- TTR per BICR

5.3.3 iRECIST Efficacy Endpoints by Investigator Assessment

For Cohort 9, additional endpoints of iBOR, iORR, iDCR, iPFS, and iDOR will be analyzed based on iRECIST guidelines.

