6.4.2.3 PFS per Investigator Assessment

PFS per RECIST Version 1.1 by investigator assessment will be summarized for each cohort in the FAS. Number and percentage of subjects with an event and each event type (death, PD), censoring and each censoring type (no event, start new anti-cancer treatment before PD or death) will be summarized. PFS will be analyzed using Kaplan-Meier methodology and Kaplan-Meier plots will be provided. The median, first quartile, third quartile and the corresponding two-sided 95% CIs will be calculated. The PFS rate at months 6, 12, 24 and 36 will be summarized along with the corresponding 95% CI if applicable.

6.4.2.4 OS

OS will be summarized for each cohort in the FAS. Number of subjects with event and censoring will be summarized. OS will be analyzed using Kaplan-Meier methodology and Kaplan-Meier plots will be provided. The median, first quartile, third quartile and the corresponding two-sided 95% CIs will be calculated. The OS rate at months 6, 12, 24, 36 will be summarized along with the corresponding 95% CI if applicable.

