6.4.3.2 Endpoints per RECIST Version 1.1 by BICR

For cohorts with imaging scans read by BICR as defined in Section 5.3.2, confirmed ORR per BICR, DOR per BICR, DCR per BICR, PFS per BICR, BOR per BICR and TTR per BICR will be analyzed in the same way as the corresponding endpoints per investigator assessment as described in Sections 6.4.1 and 6.4.2.

Analyses based on RES population will require subjects to have measurable disease at baseline per BICR.

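### In cohorts 1 to 8, scans stop at investigator-assessed progression, so PFS and DOR per BICR informatively censor subjects whose progression the central reader did not call; the plan neither counts them nor tests the effect

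*Protocol*

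**What the plan says.** **When scans stop.** For cohorts 1 to 8, Protocol 1.1 (repeated in 4.1 and 7.1.1) continues imaging "until the subject has radiologically-confirmed disease progression, initiates a new subsequent anticancer therapy, dies, withdraws consent, is lost to follow-up or the study closes". Protocol 7.1.1 names who decides: "Disease response and progression will be assessed by the investigator". The term does not imply a second scan. Protocol 7.1.3 gives mandatory confirmation of progression as a feature of iRECIST that RECIST 1.1 lacks. After progression, Protocol 7.1.5 provides only survival contact every 12 weeks.

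**When central reads happen.** Protocol 7.1.1 states: "Images at the independent review facility will be stored". A cohort may be read centrally once its stage 1 responder minimum is met, or at the sponsor's discretion. No central read is required before imaging ends.

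**How the BICR endpoints are built.** SAP 5.3.2 derives them like the investigator endpoints, "except that timepoint tumor response per independent central review will be used". SAP 6.4.3.2 adds that they "will be analyzed in the same way as the corresponding endpoints per investigator assessment". The inherited PFS rule in SAP 5.2.3 is: "If a subject has neither PD nor death, PFS will be censored at the date of last evaluable radiological tumor assessment". SAP 5.2.1 has the parallel rule for DOR. Both sections count death as an event, but censor if new anti-cancer treatment came first or if the death follows two or more consecutive missed assessments.

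**What is reported.** SAP 6.4.2.3 says "censoring and each censoring type (no event, start new anti-cancer treatment before PD or death) will be summarized". SAP 6.4.2.1 lists the same two types for DOR. No count of reader disagreement and no sensitivity analysis for it is planned.

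**The concern.** Kaplan-Meier estimation assumes that a censored subject has the same future risk as those still under observation. Here the censoring is triggered by the investigator seeing progression. The subjects removed are those most likely to have been called PD centrally at the next scan, had there been one. The more often the central reader does not call the investigator's PD, the longer central PFS and DOR appear.

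The planned output would hide this. Such a subject falls under no event or under new treatment, together with subjects who really were progression-free.

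The SAP already handles a parallel case differently. In Table 1 of SAP 5.3.3.4 (iPFS, cohort 9), an unconfirmed progression with no later scan, in a subject no longer in response follow-up, is an event at that date. PFS and DOR per BICR in cohorts 1 to 8 have no such rule, even as a sensitivity analysis.

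**Working it through.** The documents give no planning figure for PFS or DOR per BICR, so there is nothing to reproduce. The calculation below shows direction and scale only.

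**Direction.** Let L be the hazard of investigator PD, q the share of those PDs not called centrally, and kL the hazard of central PD after investigator PD had scans continued.
- Scans stopped, subject censored: the central PD hazard among those still scanned is L(1−q), so the median is ln 2 / [L(1−q)].
- Scans continued: S(t) = exp(−Lt) + q[exp(−Lt) − exp(−kLt)]/(k−1).
- With k = 1−q the second expression reduces to exp(−(1−q)Lt), the same curve. So there is no bias only if a subject just called PD by the investigator has no higher central PD hazard than subjects still being scanned. Any larger k biases upward.

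Ratio of stopped-scan to continued-scan median:

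| q | k=1 | k=2 | k=4 | k=8 |
|---|---|---|---|---|
| 0.1 | 1.00 | 1.04 | 1.07 | 1.09 |
| 0.2 | 1.02 | 1.09 | 1.15 | 1.20 |
| 0.3 | 1.05 | 1.16 | 1.27 | 1.35 |

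**Scale for DOR.**
- From the documents: median DOR 9.4 months (cohort 5, investigator-assessed, Protocol 2.4.1) and a 56-day scan interval, 56/30.4375 = 1.84 months. The later change to 84 days is ignored.
- Assumed: discordance d of 10, 20 or 30%; central PD exactly one scan later had scans continued; no early deaths.

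Per-scan hazard: h = 1 − 0.5^(1.84/9.4) = 0.127, so h/(1−h) = 0.145.
- SAP rule: median = 1.84 × ln(0.5)/ln(1 − h(1−d)).
- Continued scans: median = 1.84 × ln[0.5/(1 + d·h/(1−h))]/ln(1−h).

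| d | SAP rule (months) | Continued scans (months) |
|---|---|---|
| 10% | 1.84 × 5.72 = 10.5 | 1.84 × 5.22 = 9.6 |
| 20% | 1.84 × 6.48 = 11.9 | 1.84 × 5.32 = 9.8 |
| 30% | 1.84 × 7.45 = 13.7 | 1.84 × 5.42 = 10.0 |

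These medians come from smooth curves. With real scan dates the observed median falls on a scan day and may not move. A simulation with 56-day scans, deaths, new therapy and the two-missed-scan rule gave median ratios from about 0.99 (noise at k=1) to 1.36 for q of 0.1 to 0.4, with many cells at 1.00.

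**Effect of early deaths.** Suppose 30% of discordant subjects die in time to count (also assumed), taken as events at the investigator-PD scan. Then d = 0.20 becomes 0.20 × 0.7 = 0.14, and the SAP-rule median falls from 11.9 to about 11.0 months. The excess over 9.8 drops from 2.1 to about 1.2 months.

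**Sampling error for comparison.** Cohort 5 had 11 responders (1 CR, 10 PR). With exponential times the sample median is the 6th of 11, and the 2.5% and 97.5% points of Beta(6,6) are 0.234 and 0.766. With mean 9.4/ln 2 = 13.56 months, the 95% range is −13.56 × ln(1−0.234) = 3.6 to −13.56 × ln(1−0.766) = 19.7 months.

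**The case against.** **Low stakes.** For cohorts 1 to 8 the BICR endpoints are exploratory and the central read is optional. Protocol 7.1.1 says the study is analysed on local assessments. This stands, and it limits the point to a cheap improvement.

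**Weak link to the decision.** A reader might infer that the bias feeds the conclusion that a cohort is promising. Protocol 9.11 and SAP 6.7 set that rule as a responder count. They mention central imaging data only as something taken into account, and neither names PFS or DOR per BICR. The documents do not support the stronger inference.

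**The lower end for PFS already exists.** If the central reader is never earlier than the investigator, counting these subjects as events at investigator PD reproduces investigator PFS, which is already reported on the same FAS. This stands. For PFS the new information is mainly the count. For DOR the set of central responders can differ, so an extra curve adds something.

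**Noise.** With 11 responders, sampling error dwarfs a two-month shift. That is true of one cohort's median, but a one-directional error does not average out, and readers would not know it was there.

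**Opposite disagreement.** Earlier central PD lowers the estimate, so disagreement in general does not inflate it. Only investigator PD without central PD does.

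**Conclusion.** For cohorts 1 to 8 the mechanism follows from the documents, and the bias in PFS and DOR per BICR is upward whenever subjects just called PD by the investigator carry a higher central PD hazard than those still being scanned. The size cannot be derived. The excess of about 1 to 4 months in median DOR (10.5 − 9.6 to 13.7 − 10.0) rests on assumed discordance, a one-scan lag and no early deaths.

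Four stronger readings are tempting and not supported:
- That only central PD counts as an event. Death also counts, within the limits in SAP 5.2.1 and 5.2.3.
- That no later scan can exist. Protocol 7.1.1 permits additional imaging to confirm suspected progression, though it does not require it.
- That the urothelial example in Protocol 2.2.1.3 ("there was a loss of 1 responder when an equivocal new lesion identified at week 8 became unequivocal at a later time point") shows this mechanism. That passage does not say that the investigator had called PD or that scans had stopped.
- That the whole study is affected. The primary endpoint and investigator PFS and DOR are not, and cohort 9 is partly protected because its scans run to iCPD.

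**What to change.** In SAP 6.4.3.2, for cohorts 1 to 8:

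1. Add a censoring category, investigator PD without BICR PD, and report its count for both PFS and DOR per BICR.
2. Prespecify, for analyses still to come, a sensitivity analysis of DOR per BICR in BICR responders that counts investigator PD as the event for these subjects. Show it beside the censored analysis.
3. For PFS per BICR, present investigator PFS alongside as the approximate lower bound, or run the same sensitivity analysis where central PD can precede investigator PD.

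The cohort 5 primary analysis was completed on 27 Jul 2022 (Protocol 2.4.1), so for that cohort the change can reach only later analyses, such as the final analysis in SAP 6.8.

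The cost is SAP wording and one extra Kaplan-Meier run, or two if PFS is rerun, with no new scans or reads. The downside is that the sensitivity result is a lower bound and may slightly understate central durability. In the illustration it would give 9.4 months, against 9.6 to 10.0 with continued scans.

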1.2 Study Schema
Figure 1 Cohorts 1 to 8 Study Schema

*Subjects initially enrolled in Cohort 6 will be reallocated to Cohort 7 or 8 based on tumor type/histology. Disease assessment will be performed at screening/baseline and repeated every 8 weeks (56 days ± 7 days) from the first dose of study treatment throughout the study until the subject has radiologically-confirmed disease progression, initiates a new subsequent anticancer therapy, dies, withdraws consent, is lost to follow-up or the study closes, whichever comes first. A confirmatory imaging scan is required 4 weeks (28 days + 7-day window) after the first response. After 1 year on study treatment, the frequency of response assessments will be reduced to every 12 weeks (84 days ± 7 days).

Figure 2 Cohort 9 Schema

CPS: combined positive score; HNSCC: head and neck squamous cell carcinoma; PD-L1: programmed death-ligand 1

- 1 Local PD-L1 test results may be used for eligibility and should be submitted to confirm positive PD-L1 status (CPS ≥1). If Local testing is unavailable then archival or fresh tissue must be submitted for central testing prior to enrollment; central PD-L1 testing results will be required prior to subject enrollment.
- 2 Disease assessment will be performed at screening/baseline. The first on-study disease assessment will be 9 weeks (± 7 days) from the first dose of study treatment and then every 6 weeks (± 7 days) throughout the study until the subject has radiologically-confirmed disease progression, initiates a new subsequent anticancer therapy, dies, withdraws consent, is lost to follow-up or the study closes, whichever comes first. A confirmatory imaging scan is required 4 weeks (28 days + 7-day window) after the first response. After 18 months on study treatment, the frequency of response assessments will be reduced to every 9 weeks (84 days ± 7 days).

1.3 Schedules of Assessments

Table 1 Schedule of Assessments – Cohorts 1 to 8

Assessments		Period	Screening/Baseline		Treatment						Follow-up				
					Cycle 1			Subsequent Every Cycle			Every 8 Weeks	EOT	30-day Safety Follow-up	Post Treatment Follow-up	Long-Term Follow-up
Cycle Day			-28 to -1	-7 to -1	1	8	15	1	8	15		Date of last dose ¹⁸	30 days from last dose	Every 8 weeks	Every 12 weeks
Visit Window (Days)			0	0	0	± 3	± 3	± 3	± 3	± 3	± 7	+ 7	+ 7	± 7	± 7
General Study Procedures															
Informed Consent			X												
Confirmation of Eligibility per Inclusion/Exclusion Criteria			X		X										
Medical History/Disease History/Demographics			X												
Subject Enrollment					X										
Tumor Tissue Sample ^{1, 2}			X												
PGx Blood Sample (optional)				X											
Pregnancy Test ³				X	X			X				X	pregnancy test monthly until 6 mo after last dose of study treatment		
Physical Examination ⁴				X	X			X				X			
Weight				X	X			X				X			
Vital Signs				X	X	X	X	X	X	X		X			
ECOG Performance Status				X	X			X				X			
PRO/QOL ⁵					X			X				X			
Survival ⁶															X
Prior/Concomitant Medications ⁷												Every visit			
AE Assessment ⁸												Every visit			
Imaging															
Brain Scan ⁹			X									X ⁹		X ⁹	
Bone Imaging ⁹			X									X ⁹		X ⁹	
Image/Disease Assessment ^{10, 11}			X									X ¹¹		X ¹¹	

Assessments	Period	Screening/Baseline		Treatment						Follow-up				
				Cycle 1			Subsequent Every Cycle			Every 8 Weeks	EOT	30-day Safety Follow-up	Post Treatment Follow-up	Long-Term Follow-up
Cycle Day		-28 to -1	-7 to -1	1	8	15	1	8	15		Date of last dose ¹⁸	30 days from last dose	Every 8 weeks	Every 12 weeks
Visit Window (Days)		0	0	0	± 3	± 3	± 3	± 3	± 3	± 7	+ 7	+ 7	± 7	± 7
Clinical Laboratory Tests ^{12, 13}														
Hematology			X ^{12, 13}	X	X ¹³	X	X				X			
Biochemistry			X ^{12, 13}	X	X ¹³	X	X				X			
Hemoglobin A1c ¹⁴			X ^{12, 13}								X			
Total cholesterol, HDL-C, LDL-C, Triglycerides			X ^{12, 13}											
Electrocardiograms														
12-lead ECG ¹⁵			X								X			
Ophthalmology														
Complete Eye Exam ¹⁶		X									X ¹⁶			
Visit Window (Days)				0	+3	+3	+3	+3	+3					
Investigational Product Dispensing/Administration														
Enfortumab Vedotin ¹⁷				X	X	X	X	X	X	X				

AE: adverse event; ECG: electrocardiogram; ECOG: Eastern Cooperative Oncology Group; EOT: end of treatment; HDL-C: high-density lipoprotein cholesterol; LDL-C: low-density lipoprotein cholesterol; PGx: pharmacogenomic; PRO: patient reported outcome; QOL: quality of life

1. Tumor tissue (from primary or metastatic site) for biomarker studies should be available for submission to the sponsor. If an archival tumor tissue sample is not available, the subject will have a biopsy to obtain tumor tissue prior to study treatment. Tumor tissue may be submitted as either a tissue block or freshly sectioned, unstained charged slides. A minimum of 10 and up to 20 slides are needed from each subject for the planned biomarker studies. If at least 10 slides cannot be sectioned from available block, please provide as many as possible and discuss with the sponsor. If multiple blocks will be used to produce slides, please contact the sponsor before cutting the blocks.
2. If any additional biopsy is performed as standard of care while on study treatment or during follow-up period, subject's tumor tissue samples are requested to be submitted as either a tissue block or freshly sectioned, unstained charged slides to the sponsor, if available.
3. For women of childbearing potential only. A serum pregnancy test will be performed at baseline. A urine or serum pregnancy test will then be repeated on day 1 of each cycle prior to study drug administration, at EOT and follow-up visits. After EOT, a monthly (±7 days) pregnancy test will be maintained until 6 months after the last dose of study treatment.
4. Full physical examination will be performed. Height measurement is only required at screening/baseline. Physical examination on cycle 1 day 1 is not necessary if it was performed within 7 days prior to the first day of dosing.
5. Quality of life questionnaires will be completed by the subject at the clinic visit prior to dosing and any other study assessments.

Footnotes continued on next page

6. After radiologically-confirmed disease progression or initiation of subsequent anticancer therapy, whichever occurs first, subjects will be contacted every 12 weeks in the long-term follow-up period for survival status until death, withdrawal of consent, lost to follow-up, or study closure, whichever occurs first. Sponsor may choose to discontinue the collection of survival status for any cohort.
7. Include all medications taken from the time of informed consent.
8. AEs will be collected from the time of informed consent through 30 days following the last dose of study treatment or until initiation of a new anticancer treatment, whichever occurs first.
9. Brain scan and bone imaging will be performed at screening/baseline. Repeat at response assessment time points if metastases were identified at screening/baseline, or if metastasis is known or suspected, or as clinically indicated throughout the study.
10. Imaging/disease assessment will be performed at screening/baseline and every 8 weeks (56 days \pm 7 days) from the first dose of study treatment throughout the study. Baseline imaging performed prior to informed consent as part of standard of care may be used as long as it is performed within 28 days prior to the first dose of study treatment. * Inclusion of neck anatomy, chest, abdomen, pelvis is required at all imaging visits for the head and neck cancer cohort, cervical/cervicothoracic junction and esophagus malignancy cancer types. Additional neck anatomy imaging should be performed as clinically indicated for all other cohorts. If neck imaging is obtained at a post-baseline timepoint, then it should be submitted at every timepoint thereafter. Copies of all imaging scans will also be sent to the independent review facility in a timely manner.
11. If disease response is assessed as complete response or partial response by investigator, a confirmatory imaging scan is required 4 weeks (28 days \pm 7-day window) after the first response. After 1 year on study treatment, the frequency of disease response assessments will be reduced to every 12 weeks (84 days \pm 7 days).
Subjects who discontinue study treatment for reasons other than consent withdrawal or radiologically-confirmed disease progression by RECIST Version 1.1 will continue to receive imaging scans every 8 weeks (56 days \pm 7 days) until subject has radiologically-confirmed disease progression, initiates a new anticancer therapy, dies, withdraws consent, is lost to follow-up, or the study closes, whichever comes first. Tumor imaging may also be performed whenever disease progression is suspected.
12. See [Appendix 12.7 Laboratory Assessments]. Clinical laboratory tests will be performed locally prior to dosing. If tests were performed within 7 days prior to the first day of dosing, they do not need to be repeated on cycle 1 day 1.
13. Clinical laboratory tests at screening and on cycle 1 day 8 are to be performed after the subject has been fasting in order to ensure accurate interpretation of lab values such as glucose values. Fasting status will be recorded in source documents. Fasting is not necessary for laboratory tests performed at all other visits.
14. If HbA1c is elevated (\geq 6.5%), refer subject to appropriate provider during cycle 1 for glucose management.
15. Prior to performing 12-lead ECGs, subjects should rest in supine position (or semi-recumbent, if supine is not tolerated) for 10 minutes. ECGs will be read and assessed locally.
16. Repeated as clinically indicated throughout the study. Include but not limited to: visual acuity, slit lamp, tonometry examination, and dilated fundus examination. EOT slit lamp examinations are only required for subjects who experience ocular AEs during the study and must be performed \geq 4 weeks from last dose.
17. At least 7 days must elapse between doses of enfortumab vedotin. Subjects should be observed during enfortumab vedotin administration and for at least 60 minutes following the infusion for the first 3 cycles.
18. The EOT visit should occur within 7 days of the last dose of enfortumab vedotin or when the decision is made by the investigator to discontinue the subject from treatment, or prior to the initiation of another anticancer therapy, whichever occurs earlier.

Table 2 **Schedule of Assessments – Cohort 9**

Assessments	Period		Screening/Baseline		Treatment						Follow-up			
					Cycles 1 and 2				Subsequent Every Cycle	Every 6 Weeks ¹¹	EOT	30-day Safety Follow-up	Post Treatment Follow-up	Long-Term Follow-up
Cycle Day			-28 to -1	-7 to -1	1	8	15	1	8		Date of last dose ₂₁	30 days from last dose	Every 9 weeks ₁₂	Every 12 weeks
Visit Window (Days)			0	0	0	± 3	± 3	± 3	-1 to + 4	± 7	+ 7	+ 7	± 7	± 7
General Study Procedures														
Informed Consent			X											
Tumor Tissue Sample ^{1,2}			X											
PD-L1 Test Result ³			X											
Confirmation of Eligibility per Inclusion/Exclusion Criteria			X		X									
Medical History/Disease History/Demographics			X											
Subject Enrollment					X									
PGx Blood Sample (optional)				X										
Pregnancy Test ⁴				X	X			X			X	Pregnancy test monthly until 6 mo after last dose of study treatment		
Physical Examination ⁵				X	X			X			X		X	
Weight				X	X			X			X			
Vital Signs				X	X	X		X	X		X			
ECOG Performance Status				X	X			X	X		X		X	
PRO/QOL ⁶					X	X	X	X	X		X	X		
Survival ⁷														X
Prior/Concomitant Medications ⁸														
AE Assessment ⁹														
Imaging														
Image/Disease Assessment ^{10, 11}			X							X ^{10, 11}			X ¹¹	

Assessments	Period	Screening/Baseline				Treatment				Follow-up		
				Cycles 1 and 2		Subsequent Every Cycle		Every 6 Weeks ¹¹	EOT	30-day Safety Follow-up	Post Treatment Follow-up	Long-Term Follow-up
	Cycle Day	-28 to -1	-7 to -1	1	8	15	1	8	Date of last dose ²¹	30 days from last dose	Every 9 weeks ¹²	Every 12 weeks
	Visit Window (Days)	0	0	0	± 3	± 3	± 3	-1 to + 4	+ 7	+ 7	± 7	± 7
Clinical Laboratory Tests ^{13,14}												
Hematology			X ^{13,14}	X ¹³	X ¹⁴	X ¹⁵	X	X	X			
Biochemistry			X ^{13,14}	X ¹³	X ¹⁴	X ¹⁵	X	X	X			
Hemoglobin A1c			X ^{13,14}						X			
Total cholesterol, HDL-C, LDL-C, Triglycerides			X ^{13,14}									
Thyroid Function Tests			X	X			X ¹⁶					
Coagulation			X									
Electrocardiograms												
12-lead ECG ¹⁷			X						X			
Ophthalmology												
Complete Eye Exam ¹⁸		X							X ¹⁸			
Investigational Product Dispensing/Administration												
Enfortumab Vedotin ¹⁹				X	X		X	X				
Pembrolizumab ²⁰				X			X					

AE: adverse event; CPS: combined positive score; ECG: electrocardiogram; ECOG: Eastern Cooperative Oncology Group; EOT: end of treatment; HDL-C: high-density lipoprotein cholesterol; iRECIST: modified RECIST v1.1 for immune-based therapeutics; LDL-C: low-density lipoprotein cholesterol; PD-L1: programmed death-ligand 1; PGx: pharmacogenomic; PRO: patient reported outcome; QOL: quality of life

1. Tumor tissue (from primary or metastatic site) for PD-L1 testing and biomarker studies should be available for submission to the sponsor. If an archival tumor tissue sample is not available for screening/baseline, the subject will have a biopsy to obtain tumor tissue prior to study treatment. Tumor tissue may be submitted as either a tissue block or freshly sectioned, unstained charged slides. A minimum of 10 and up to 20 slides are needed from each subject for the planned biomarker studies. If at least 10 slides cannot be sectioned from available block, please provide as many as possible and discuss with the sponsor. If multiple blocks will be used to produce slides, please contact the sponsor before cutting the blocks.
2. If any additional biopsy is performed as standard of care while on study treatment or during follow-up period, subject's tumor tissue samples are requested to be submitted as either a tissue block or freshly sectioned, unstained charged slides to the sponsor, if available.

Footnotes continued on next page

3. Local PD-L1 test results may be used for eligibility and should be submitted to confirm positive PD-L1 status ($\text{CPS} \geq 1$). If Local testing is unavailable then archival or fresh tissue must be submitted for central testing prior to enrollment; central PD-L1 testing results will be required prior to subject enrollment.
4. For women of childbearing potential only. A serum pregnancy test will be performed at baseline. A urine or serum pregnancy test will then be repeated on day 1 of each cycle prior to study drug administration, at EOT and follow-up visits. After EOT, a monthly (± 7 days) pregnancy test will be maintained until 6 months after the last dose of study treatment.
5. Full physical examination will be performed. Height measurement is only required at screening/baseline. Physical examination on cycle 1 day 1 is not necessary if it was performed within 7 days prior to the first day of dosing.
6. Quality of life questionnaires will be completed by the subject at the clinic visit prior to dosing and any other study assessments.
7. After radiologically-confirmed disease progression or initiation of subsequent anticancer therapy, whichever occurs first, subjects will be contacted every 12 weeks in the long-term follow-up period for survival status until death, withdrawal of consent, lost to follow-up, or study closure, whichever occurs first. Sponsor may choose to discontinue the collection of survival status for any cohort.
8. Include all medications taken from the time of informed consent.
9. AEs will be collected from the time of informed consent through 30 days following the last dose of study treatment. SAEs related to pembrolizumab will be collected from Day 1 through 90 days after the last study treatment, or 30 days following cessation of study treatment if the subject initiates a new anticancer therapy.
